1. A questionnaire addressing pain quantity will be used. A validated 0 through 10 scale, with 0 being no pain and 10 being severe pain that is disabling; unable to perform Activities of Daily Living. Additionally, background

Title: Does Alkalization of Technetium-99m Sulfur Colloid reduce perceived pain levels during non-breast sentinel lymphoscintigraphy?

PI: [name]

information will be collected for subset analysis.

VI. Study Population

- A. Recruitment: Serial voluntary enrollment of 60 subjects.
- B. Study population: All patients, age 18 years and older, who present to UAMS NM DEPT for SLN evaluation.
- C. Inclusion criteria:
 1. Male and female patients of all races and ethnicities, age 18 years and older, presenting for SLN imaging for melanoma or who have had an excisional biopsy for melanoma of the thorax and appendicular structures;
 2. Patients scheduled to receive two or more injections of Tc-99m SC for the purpose of clinical management of melanoma or who have had an excisional biopsy for melanoma of the thorax and appendicular structures.
- D. Exclusion criteria:
 1. All patients presenting for SLN imaging of lesions involving the breast, ear, nose, and genitourinary regions;
 2. Patients scheduled to receive only a single injection of Tc-99m SC;
 3. All pregnant or breast feeding women. Women will be screened according to UAMS NM DEPT routine operating procedures prior to being considered for enrollment. Subsequently, only women who are found to be non-pregnant AND non-breast feeding will be invited for enrollment.

VII. Risks and Benefits

- A. Risks:
 1. Loss of patient personally identifiable information: In order to mitigate this, investigators shall maintain all personally identifiable information in accordance with UAMS policies. Moreover, only the primary investigator will have access to the code that identifies the subjects.
 2. Listed potential adverse reactions include:
 - a. For Tc-99m: Cardiopulmonary arrest, seizures, anaphylactic shock, hypotension, dyspnea, abdominal pain, fever, chills, bronchospasm, nausea, vomiting, perspiration, redness, urticaria, numbness, dizziness and burning at the injection site. Several deaths and cases of lung and soft tissue uptake other than RES have been reported in association with the use of Technetium Tc 99m Sulfur Colloid Injection.
 - b. For Sodium Bicarbonate: Chemical cellulitis.

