- A. Planned Data Analysis: Reported pain responses to SOC and pH altered injections will be assessed using a basic cross-over design. Specifically, the two treatments will be studied within each subject; however, the sequence in which subjects will receive treatment will be randomized. Subjects randomized to one sequence group will receive the SOC injection first followed by the pH altered, while the other sequence group will receive pH altered then SOC injections. The following table succinctly presents this design.

Period	Sequence Group	
	A	B
1	SOC	pH altered
2	pH altered	SOC

In addition to the effect of treatment, the statistical model used to analyze this data must account for the effect of the sequence group, as well as the effect of *period*; therefore, the following mixed-effect analysis of variance model is proposed:

$$Y_{ijk} = \mu + \text{SEQ}_i + \text{sub}_{ij} + \text{PER}_k + \text{TRT}_h + e_{ijk}, \text{ where}$$

Y_{ijk} is the pain assessment for the j th subject during the k th period in the i th sequence group ($i = 1, 2$; $j = 1, 2, \dots, n_i$; $k = 1, 2$), SEQ_i is the effect of the i th sequence group, sub_{ij} is the effect of the j th subject in the i th sequence, PER_k is the effect of the k th period, TRT_h is the effect of the h th treatment ($h=1, 2$), and e_{ijk} is the error. The sequence, period and treatment effects will be modeled as fixed effects, while the subject effect and the error will be modeled random effects. An α -level of 5% will be used to determine the statistical significance of the treatment effect, as well as the other fixed effects.

One potential shortcoming of the proposed cross-over design is that the pain assessments will be made within minutes of one another; thus, a period or “carry-over” effect may be present. The proposed model will be able to detect such effects and, if present, only data from the first period will be used to evaluate the effect of treatment. In this case, the model reduces to a simple two-sample t-test.

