- B. Sample Size Justification: We wish the study to be sufficiently powered in the event that a significant “carry-over” or period effect is detected and only the first period data is used to evaluate the effect of treatment. To this end, the following sample size calculation is based on a two-sample t-test. A recent study by Stojadinovic et al. reported a pain scale standard deviation of 2.65 for a SOC group. We anticipate that the pH adjusted group will reduce pain, on average, by 2 points. Given this information, a two-sample t-test will have over 80% power to detect this difference assuming 30 subjects per group (60 in total) are enrolled. (It should be noted that if no carry-over effect is detected and both periods are

Title: Does Alkalization of Technetium-99m Sulfur Colloid reduce perceived pain levels during non-breast sentinel lymphoscintigraphy?

PI: [name]

used in the analysis, the proposed sample size will provide the test of the treatment effect with over 98% power to detect a 2 point difference and with over 80% power to detect a 1 point difference).

C. Randomization: To ensure the number of subjects randomly assigned to each sequence group is equal, the technique of permuted block randomization will be employed. The randomization procedure will also be stratified according to the following, broadly defined sites of injection:

1. Thorax, including neck and buttocks;
2. Head;
3. Appendicular structures, including shoulder to wrist, including back of hand, and hip to ankle;
4. Other (remainder of hand and feet).

Randomization will be applied independently within each stratum. That is, a separate randomization “schedule” will be applied within each stratum. This will ensure that the injection site distribution of the sequence groups will be similar.

XII. Ethical Considerations

- A. This study will be conducted in accordance with all applicable government regulations and University of Arkansas for Medical Sciences research policies and procedures. This protocol and any amendments will be submitted and approved by the UAMS Institutional Review Board (IRB) to conduct the study.

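### Switching to a first-period t-test when sequence or period is significant raises the null type I error from 5% to about 6% to 8%, and discards period 2 for a period effect the model already handles

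*Combined protocol and SAP*

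**What the plan says.** Section XI.A (Planned Data Analysis) fits a mixed model to the first two injections, with sequence, period and treatment fixed and subject random. A "level of 5% will be used to determine the statistical significance of the treatment effect, as well as the other fixed effects". Because the scores are taken close together, XI.A warns that "a period or “carry-over” effect may be present" and continues: "The proposed model will be able to detect such effects and, if present, only data from the first period will be used to evaluate" the treatment effect. "In this case, the model reduces to a simple two-sample t-test".

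Section XI.B (Sample Size Justification) sizes the trial for that fallback, in case a carry-over "or period effect is detected and only the first period data is used to evaluate the effect of treatment". For the analysis that keeps both periods it claims "over 98% power to detect a 2 point difference and with over 80% power to detect a 1 point difference". Neither section adjusts the 5% level for the preliminary tests.

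The model has no carry-over term, so the sequence term is the only one in which carry-over could show. The protocol does not say so; this is an inference, but the rule cannot be operated otherwise.

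**The concern.** Three things look wrong.

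1. The preliminary sequence test and the fallback t-test are computed partly from the same scores. Choosing the second because the first was significant selects trials in which the first-period difference is already large by chance, so the treatment test would not hold its 5%.
2. Carry-over is judged between subjects, on subject totals, where the design is weakest. The assurance that the model can detect it needs support.
3. A period effect common to both sequences does not bias the two-period treatment estimate, because period is a model term. Discarding period 2 for that reason gives up the within-subject comparison for nothing.

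At stake is the trial's only stated efficacy comparison: its error rate, its power, and which data it uses.

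**Working it through.** **Inputs.** From XI.A: 5% for every fixed effect, and a switch on period or carry-over. From XI.B: SD 2.65, 30 per sequence, differences of 2 points and 1 point. Assumed, because the protocol does not give them: two-sided tests, within-subject correlation ρ of 0, 0.3, 0.5 and 0.7, and the sizes of period and carry-over effects.

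**The plan's own figures.** First-period SE = 2.65 × √(2/30) = 0.684. For 2 points, 2/0.684 = 2.92, which gives 82% power on 58 df and agrees with the stated figure of over 80%. For 1 point the same test has 30%. Two-period SE = 2.65 × √(2(1−ρ)/60), which is 0.342 at ρ = 0.5; for 1 point, 1/0.342 = 2.92, again 82%. The claim of over 80% at 1 point therefore implies ρ of roughly 0.47 or more.

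**Why the error rises.** The sequence contrast and the first-period difference have correlation √((1+ρ)/2), which is 0.71 at ρ = 0 and 0.92 at ρ = 0.7. Under the full null at ρ = 0.5, simulation shows the fallback rejecting in 53% of the trials with a significant sequence test. The parts add up as follows:

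- Sequence significant: 5% × 53% = 2.65%.
- Period significant, sequence not: 5% × 95% = 4.75% of trials. The first-period test rejects in 5% overall, so without a significant sequence test it rejects in about (5 − 2.65)/95 = 2.5%. Contribution: 0.12%.
- Neither significant: 95% × 95% = 90.25% of trials, at about 5%. Contribution: 4.51%.

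The total is about 7.3%. Simulation gives 7.2%; the sum is approximate because the period and treatment tests share one variance estimate.

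**Simulation of the rule as written** (400,000 null trials per correlation; 40,000 to 200,000 for other scenarios). The last three columns assume a true 1-point period effect.

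| ρ | Null type I error | Fallback rejects, given significant sequence (null) | Trials that switch | Power for 1 point: rule / two-period model | Power for 2 points: rule / two-period model |
|---|---|---|---|---|---|
| 0 | 6.3% | 33% | 55% | 40% / 53% | 89% / 98% |
| 0.3 | 6.8% | 44% | 70% | 42% / 68% | 87% / 99.8% |
| 0.5 | 7.2% | 53% | 83% | 39% / 82% | 85% / >99.9% |
| 0.7 | 7.8% | 63% | 96% | 33% / 96% | 83% / >99.9% |

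The null error is 8.0% at ρ = 0.8 and 8.7% at 0.95. Switching on sequence alone gives 6.4% to 8.2% for ρ from 0 to 0.8; switching on period alone stays at about 5.0%. Rounding and clipping scores to the 0–10 scale gives similar results (6.9%, 7.0% and 7.9% at ρ = 0.3, 0.5 and 0.7).

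**The power loss by hand, ρ = 0.5.** The period contrast has the same SE as the treatment contrast, so a 1-point period effect is detected in 82% of trials. With the 5% from sequence, the switch occurs in 1 − 0.18 × 0.95 = 83%. Power for 1 point is then about 0.83 × 30% + 0.17 × 82% = 39%.

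**Detecting carry-over.** Sequence SE = 2.65 × √(2(1+ρ) × 2/30), which is 1.185 at ρ = 0.5. A 1-point carry-over difference is 1/1.185 = 0.84 SE, giving 13% power. Over ρ from 0 to 0.7, power is 12% to 17% for 1 point and 34% to 53% for 2 points. An undetected carry-over difference shifts the two-period estimate by half its size, so 1 point shifts it by 0.5. The benefit is understated if the less painful solution also leaves less residual pain, and overstated in the opposite case. With no direct effect and a 1-point carry-over, the rule declares an effect in 14% to 25% of trials (carry-over in one sequence only) or 16% to 41% (split evenly between sequences).

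**The case against.** The strongest reply is that the unconditional two-period model does worse in the very situation XI.A fears. With a 1-point carry-over and no direct effect it rejects in 17%, 23%, 30% and 46% of trials across the four correlations, more than the present rule. Add a 1-point period effect and, at ρ = 0.5, the rule rejects in 5% to 9% against 30% for the two-period model, because the period trigger sends most trials to the unbiased first-period test. This is correct. It is an argument for making the first-period test primary outright, not for reaching it through a preliminary test.

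Other points carry weight:

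- The inflation applies when there is no period effect. With a true 1-point period effect, type I error is 5.0% to 5.6%.
- The fallback was deliberately powered for 2 points, and the rule keeps 83% to 89% there even with a 1-point period effect. The heavy loss is at 1 point, which XI.B mentions only in a parenthesis.
- That parenthesis makes the two-period analysis depend on carry-over alone, while XI.B's opening sentence names either effect. If only sequence triggers the switch, the period-related power loss largely disappears, but the type I inflation remains.
- Correlations of 0 and 0.3 sit below the roughly 0.47 that XI.B's power claim implies. Restricting to the plan's own range raises the null error to about 7% or more.

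**Conclusion.** The concern holds. Under no treatment, period or carry-over effect, the rule has a type I error of about 6% to 8% for correlations of 0 to 0.8, and about 7.2% near the correlation implied by XI.B, against a stated 5%. The excess comes from the sequence trigger and is present on either reading of the rule. The period trigger costs power instead: with an assumed 1-point period effect at ρ = 0.5, power falls from 82% to 39% for 1 point and from over 99.9% to 85% for 2 points. The claim that the model can detect carry-over is not supported for differences of 1 point, nor reliably for 2. These sizes rest on SD 2.65, 30 per sequence, two-sided tests and the assumed correlations and effect sizes; the direction of the type I inflation does not depend on the particular correlation. The rule must be corrected before any unblinded data are seen.

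**What to change.** Delete the switch in XI.A and name one primary analysis, to be used whatever the sequence and period tests show. There are two sound choices:

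- **Two-period mixed model, always.** It holds 5% under any period effect and has 82% power for 1 point at ρ = 0.5. Report the first-period t-test as a labelled sensitivity analysis that cannot replace it. The price is reliance on small differential carry-over, as the rejection rates of 17% to 46% under a 1-point carry-over show.
- **First-period t-test, always.** It holds 5% under any carry-over or period effect and has the 82% power for 2 points on which XI.B is already based. The price is 30% power for 1 point. If the sponsor takes carry-over between injections minutes apart seriously, this is the safer choice.

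Restate the power in XI.B for the analysis chosen, with its assumed within-subject correlation where that matters, and remove the conflict between the opening sentence and the parenthesis. The cost is wording in XI.A and XI.B, with no new subjects, data or procedures.

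Optionally, a supporting mixed model could use all scored injections, with treatment, injection number and previous-solution terms, since later injections are already randomised. It assumes additive first-order carry-over, and its precision depends on injection counts, because VI.C admits "Patients scheduled to receive two or more injections of Tc-99m SC". At ρ = 0.5 its SE is 0.275 if all 60 subjects have four injections, 0.334 if half have four and half two, and 0.684 if all have two, against 0.342 for the two-period model.

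### Any first-period analysis omits the injection-site strata and the pre-injection pain score; adding them would cheaply gain precision but would not repair the data-driven fallback

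*Combined protocol and SAP*

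**What the plan says.** - **The fallback (XI.A).** The main analysis is a mixed model with fixed sequence, period and treatment effects and a random subject effect. A 5% level is used "to determine the statistical significance of the treatment effect, as well as the other fixed effects". If a period or carry-over effect is found, the plan continues: "if present, only data from the first period will be used to evaluate the effect of treatment". It then adds: "In this case, the model reduces to a simple two-sample t-test". No covariate is named in either model.
- **The sample size (XI.B).** The trial is sized for the fallback: "the following sample size calculation is based on a two-sample t-test". With SD 2.65, a 2-point difference and 30 per group, "a two-sample t-test will have over 80% power to detect this difference". With both periods, the design is credited "with over 98% power to detect a 2 point difference and with over 80% power to detect a 1 point difference".
- **The strata (XI.C).** "The randomization procedure will also be stratified according to the following, broadly defined sites of injection": thorax, head, appendicular and other. The stated purpose is balance: "This will ensure that the injection site distribution of the sequence groups will be similar".
- **The baseline score (V.A.2, repeated in VIII.A).** Subjects rate pain on the 0 to 10 scale before the first injection as well as after each one. No section puts this score into a model.

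**The concern.** In the cross-over model, treatment is compared within subjects, so the subject effect absorbs stable differences due to injection site or baseline pain. The first-period test compares different subjects, and nothing absorbs those differences.

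Two things follow if the variables predict pain:

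- **Site.** Stratified randomisation balances site between the groups, so the true variance of the group difference shrinks. The t-test still counts the between-site variation in its standard error. Its size therefore falls below 5% and power is lost.
- **Baseline pain.** This is not a stratification factor, so leaving it out costs power only. Size stays at 5%.

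The first-period test is the one the trial is sized on, and its margin over 80% is about 2 points.

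**Working it through.** **Inputs.** From XI.B: SD 2.65, difference 2 points, 30 per group. From XI.A: 5% level, taken as two-sided because sidedness is not stated. Assumed, because the documents are silent: R² for site and for baseline pain, stratum sizes 24/8/24/4 split 1:1, and within-subject correlation ρ. Simulated results use 40,000 to 100,000 trials per setting.

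**1. The plan's own figure.** SE = 2.65 × √(2/30) = 0.684; noncentrality 2/0.684 = 2.92; noncentral t with 58 df gives power 82.0%. The claim of over 80% is reproduced.

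**2. Effect of omitting site, strata balanced.** The true SE is 0.684 × √(1 − R²), but the t-test uses about 0.684. At R² = 0.10 its 5% critical value of 2.00 acts like 2.00/√0.90 = 2.11, so its size is P(|t₅₈| > 2.11) = 3.9%. Adjusted power uses residual SD 2.65 × √0.90 = 2.51 and 55 df, which gives 85.7%.

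| Assumed site R² | Size, unadjusted | Power, unadjusted | Power, site-adjusted (simulated) |
|---|---|---|---|
| 0.05 | 4.4% | 82.4% | 83.8% |
| 0.10 | 3.9% | 83.2% | 85.8% |
| 0.20 | 2.8% | 84.4% | 89.4% |

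Adjusted size is 5.0% throughout. With random stratum sizes and incomplete blocks of 4 (assumed), the power gain is 1.1 / 2.5 / 5.3 points with all four strata in the model, or 0.5 / 1.2 / 2.6 points if strata under 6 are pooled.

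**3. Baseline pain.** With R² 0.10 for baseline alone, power is 82.0% unadjusted and about 85% adjusted. With site and baseline each at 0.10, residual SD is 2.65 × √0.80 = 2.37 with 54 df, and power is about 89% against about 83% unadjusted.

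**4. If neither predicts pain.** With 54 df and an allowance for chance baseline imbalance, power is 81.2% (balanced strata) or 80.9% (random stratum sizes), against 82.0% unadjusted. At 29 per group it is 79.8% against 80.6%. Break-even is at a baseline R² of about 0.02.

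**5. When these figures apply.** They describe the first-period test on its own. Whether they carry over depends on what triggers it.

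- *Period test.* Its contrast averages the within-subject changes (second minus first) over both groups. Its covariance with the first-period group difference is (ρ − 1)σ²/60 + (1 − ρ)σ²/60 = 0, so the figures carry over. The period and treatment contrasts share the SE 2.65 × √((1 − ρ)/30). XI.B's power figures therefore imply that a real period effect triggers the fallback in over 80% of trials (1 point) or over 98% (2 points).
- *Sequence test.* Its contrast uses subject sums and has correlation √((1 + ρ)/2) with the first-period difference, which is 0.87 at ρ = 0.5. The figures do not carry over.

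**6. The whole rule, ρ = 0.5.** With no true effects and site and baseline each at R² 0.10, type I error in sequence-triggered trials is about 50% unadjusted and still about 43% with both covariates. Over all trials it is about 6.4% and 6.1 to 6.3%. Adjusting for site alone, when only site is prognostic at 0.10, moves the sequence-triggered figure the other way, from 50% to 57%. With a true 2-point treatment difference and no true period effect, power of the whole rule is about 97.6% unadjusted, 97.8% with site adjustment, and 98.2% with both variables prognostic and adjusted for.

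**The case against.** The strongest reply is that nothing here is wrong. The t-test is prespecified, the sample size is built on the same test, and XI.C gives balance as the purpose of stratifying, which is achieved without a covariate. That stands, and it is why this is an optional improvement.

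Three further points also stand:

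- **The gain is hypothetical.** The documents do not show that site or pre-injection pain predicts injection pain. V.A.2 asks, before any injection, for a rating worded as the pain of each injection, so what that score measures is unclear.
- **The gain depends on the fallback.** It arises mainly when a real period effect triggers the fallback. The main model already adjusts for period, so a pure period effect is no reason to discard the second period. If the fallback is removed, this point largely disappears.
- **There is a cost.** XII.C lets subjects opt out and XI.B makes no allowance for loss. At 29 per group, uninformative covariates would put the adjusted test, but not the planned one, just below 80%.

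None of this removes the precision gain if either variable is even modestly prognostic.

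A reader might go further and infer that the t-test is invalid or the power claim overstated. The documents do not support that: the power reproduces, and the test taken alone is at worst conservative. A reader might also infer that a conservative test makes the fallback safe, or that covariates would make it so. Step 6 shows that neither is true when the sequence test is the trigger.

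**Conclusion.** The point holds as a low-severity, low-cost improvement to any first-period analysis that is kept. Taken on its own, the planned test gives up about 1 to 5 points of power for an assumed site R² of 0.05 to 0.20, and about 6 points if site and baseline each explain 10%. Its size falls below 5% only if site predicts pain. With no true period effect, power of the whole rule barely changes.

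These sizes rest on assumed R² values, stratum sizes, block size and site-effect pattern, and on 60 evaluable subjects. Choosing the analysis by a test on the same data is the larger defect, and adjustment leaves it in place.

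**What to change.** In XI.A, for any first-period analysis that is retained:

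1. Replace the t-test with a linear model of first-injection pain on treatment, injection-site stratum as randomised, and pre-injection pain score. A sparse stratum does not prevent fitting; if strata are to be pooled, fix the rule before unblinding from total stratum counts only.
2. Keep the unadjusted t-test as a sensitivity analysis.
3. State that the adjustment improves precision only, and that the type I error arising from the data-driven choice of analysis is handled separately.

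The wording of the pre-injection pain question should also be made clear, so that the covariate has a defined meaning.

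**Cost.** About three sentences and no new data. Residual degrees of freedom fall from 58 to 54. If neither variable predicts pain, power drops by about one point, to about 81% with 60 evaluable subjects and to 79.8% at 29 per group.

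### Does the claim of over 80% power for a 1 point difference in section XI.B conflict with the stated SD and the 98% figure beside it?

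*Combined protocol and SAP*

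**What the plan says.** Section XI.B (Sample Size Justification) sizes the trial on its fallback analysis, a two-sample t-test on first-period data only. It takes the SD from the cited trial of pH-adjusted radiocolloid, which "reported a pain scale standard deviation of 2.65 for a SOC group". The target effect is set by "We anticipate that the pH adjusted group will reduce pain, on average, by 2 points". From these, "a two-sample t-test will have over 80% power to detect this difference", "assuming 30 subjects per group (60 in total) are enrolled".

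A parenthetical remark then covers the case where both periods are used: the same 60 subjects give the treatment test "with over 98% power to detect a 2 point difference and with over 80% power to detect a 1 point difference".

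Section XI.A (Planned Data Analysis) describes the both-period analysis. It states that "the two treatments will be studied within each subject", and the mixed model has fixed sequence, period and treatment effects, "while the subject effect and the error will be modeled random effects". Treatment is therefore tested within subject. Neither section gives a within-subject correlation, a within-subject error SD or an SD of paired differences.

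**The concern.** The power of a within-subject comparison depends on the SD of the paired differences, not on the SD of scores across subjects. The plan gives only the latter. A reader who tries to recover the two both-period figures finds that each is closely matched by a different assumption. With no correlation, 2.65 gives 98.2% for 2 points, which fits the first figure, but 52.9% for 1 point. With 2.65 taken as the SD of the paired differences, it gives 82.0% for 1 point, which fits the second figure, but 99.99% for 2 points.

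If the plan had mixed the two assumptions, it would be promising a sensitivity to a 1 point effect that it may not have. A null result might then be taken as evidence against a 1 point benefit when the chance of detecting one was close to even.

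**Working it through.** **Inputs.** From XI.B: SD 2.65, 30 subjects per sequence group (60 in total), differences of 2 points and 1 point. From XI.A: 5% significance level. Assumed, because the plan does not say: a two-sided test, the same SD under both solutions, and complete data on all 60. The within-subject correlation ρ is not given, so it is varied.

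**Step 1: the figure that sets the sample size.** First period only, two-sample t-test, 58 df:

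- SE = 2.65 × √(2/30) = 0.684
- Noncentrality for 2 points = 2 / 0.684 = 2.92
- Power = 82.0% (noncentral t); 83.2% by normal approximation

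The plan's figure of over 80% reproduces.

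**Step 2: both periods.** With equal sequence groups:

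- SD of paired differences = 2.65 × √(2(1 − ρ))
- SE of the treatment effect = 2.65 × √(2(1 − ρ)/60), 58 df

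For ρ = 0, SE = 2.65 × √(2/60) = 0.484, so the noncentrality is 4.13 for 2 points and 2.07 for 1 point. For ρ = 0.5, SE = 2.65/√60 = 0.342, so it is 5.85 and 2.92.

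| ρ | Power, 2 points | Power, 1 point |
|---|---|---|
| 0 | 98.2% | 52.9% |
| 0.2 | 99.5% | 62.3% |
| 0.3 | 99.8% | 68.1% |
| 0.4 | 99.95% | 74.7% |
| 0.474 | 99.99% | 80.0% |
| 0.5 | 99.99% | 82.0% |
| 0.6 | >99.99% | 89.5% |

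At ρ = 0.5 the SD of the differences equals 2.65. Effect and SE are then both half of their values in Step 1, with the same 58 df, so the 1 point power matches the first-period power for 2 points at 82.0%.

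**Step 3: where each statement holds.** The 2 point statement holds for every ρ of 0 or more. The 1 point statement holds once ρ reaches 0.474, where the SD of differences is 2.65 × √(2 × 0.526) = 2.72. Every ρ from 0.474 upwards makes both statements true together. With a one-sided 5% test the threshold for 1 point falls to about 0.33.

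**Step 4: does the 98% figure fix ρ at zero?** If 98% were an exact value, the SD of differences would be 3.80 and 1 point power 51.9%, and the two figures would indeed clash. The plan gives it as a floor, and a floor of 98% is compatible with 99.99%.

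**The case for a change.** The strongest argument for acting is the pattern of the numbers. A power of 99.99% is not usually reported as over 98%, whereas 98.2% is, and that is what 2.65 gives with no correlation. It is quite possible that the two figures came from different calculations. The 1 point power is also the one that depends heavily on the missing input: between ρ = 0 and ρ = 0.5 it runs from 53% to 82%, while the 2 point power stays above 98%. And if XI.A's fallback to first-period data is triggered, 1 point power is only about 30% (noncentrality 1/0.684 = 1.46).

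Part of this stands. The 1 point figure cannot be checked from the stated inputs, and it needs an unstated correlation of about 0.47 or more. The inference that zero correlation was used does not stand. Nothing in the documents says so, and it sits awkwardly with a model that includes a random subject effect and with scores given by one person within minutes. This makes positive correlation the natural expectation; it does not show that the value reaches 0.474. The fallback figure does not contradict the plan either, because the 1 point remark is expressly conditional on both periods being used.

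The feared misreading of a null result is not something the plan sets up. It names no 1 point target and no rule that treats a null result as excluding that effect. A null result would be judged from the confidence interval and the observed within-subject variance.

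**Conclusion.** The concern does not call for a change. The arithmetic behind it is correct, but it shows an undocumented assumption, not a wrong or contradictory figure. Both power statements are lower bounds, and both are true for any within-subject correlation of about 0.474 or more (SD of differences at most about 2.72). The 2 point statement is true for any correlation of 0 or more.

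The 1 point remark is an aside. The sample size rests on the first-period comparison for the anticipated 2 points, which reproduces at 82.0%, and no analysis, decision rule or conduct step uses the 1 point figure. Writing down the correlation would be tidier reporting but would leave the 60 subjects, the model and the results as they are. A reader wanting the 1 point power can treat it as conditional: 53% at ρ = 0, 68% at ρ = 0.3 and 82% at ρ = 0.5.

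This rests on a two-sided 5% test, an SD of 2.65 under both solutions and all 60 subjects contributing both periods. The true correlation is unknown from the documents, so the 1 point claim is neither confirmed nor refuted.
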